Static balance and CSM. One area with a high potential to advance sensitivity, selectivity and gradations of CSM is a measure of static balance. Balance is the ability to maintain stable postural sway that does not exceed the limits of stability. Balance arises through the integration of sensory (somatosensory, vestibular, and visual inputs) and motor components (flexors, extensors). Sway, measured through center of pressure (COP), is a necessary component of posture as well as a well-established metric of postural control. Excessive sway is a sign of instability which may arise through sensory disturbances, motor dysfunction, or environmental perturbations.

Disturbances of postural control are hallmarks of CSM ²² and are a consequence of abnormalities in proprioception due to dorsal column or spinocerebellar tract damage of the spine ²³ or postural commands to motor neurons ^{24, 25}. Those presenting to the emergency room for head trauma from falling were more likely to have CSM ²⁶. Similarly, those hospitalized for hip fracture were more likely to also have evidence of CSM than similarly aged individuals having elective hip arthroplasty ²⁷. Further, CSM increases the risk of subsequent injury after hip replacement ²⁸. Early detection could serve to decrease rates of injury and compound injury.

Nardone et al. ²⁴ studied body sway of patients with severe CSM and cervical spondylosis without myelopathy using a force platform under conditions of eyes open or closed on a level firm surface compared to healthy controls. COP sway area was greater in both clinical groups under both eyes open and eyes closed conditions, suggesting disturbances of ascending proprioceptive input and impaired

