Although we have yet to examine posturography in veterans with CSM, [name] and [name] have active collaborations to study posturography in active duty military (*Military Medicine* in press) and veterans. We are currently conducting a study of posturography at the Syracuse Veterans Affairs Medical Center (SVAMC) in veterans as a function of lifetime mild traumatic brain injury (mTBI) and posttraumatic stress disorder (PTSD). In the interim between initial submission and revision, two veterans with MS volunteered for the study. Although the study has a different focus, the data illustrates the sensitivity of the VETS to subtle differences in balance. No veteran in the study to date has registered a self-reported problem with balance. Figure 2 depicts COP sway for otherwise **HEALTHY** (N = 10), lifetime mTBI (N = 7) and MS (N = 2) veterans under the six conditions. In observing the otherwise **HEALTHY** veterans (open bars), one can see that the foam condition places a substantial burden on balance compared to firm conditions. Further, eyes closed conditions exacerbate COP sway area, especially on foam. One can also see that the ranges of COP sway area in normal

VETS device - Six postural test conditions

Figure 1. VETS - a VR-based balance assessment device tests six conditions. Top row shows the firm support conditions and the bottom row shows the unstable (foam) support conditions. From left to right, the three columns are eyes-open (EO) while viewing a static visual scene, eyes-closed (EC) in front of a dark screen, and EO viewing a dynamic rotating screen.

[figure not shown]

Figure 2. Comparison of VETS COP sway area in SVAMC veterans as a function of history of mTBI and MS. Legend is contained in the figure. The visual conditions were eyes open (EO), eyes closed (EC) and viewing a dynamically rotating science (DYN). These visual conditions were as on Firm and Foam surface. Veterans with lifetime history of mTBI exhibited greater COP sway area during the DYN-FOAM condition compared to HEALTHY veterans. MS veterans displayed greater COP sway area during the EC conditions, and the DYN-FOAM condition compared to HEALTHY veterans.

HEALTHY veterans provide substantial room to detect abnormalities. It is against this background that we will be assessing balance disturbances in CSM.

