5.2 Recruitment Methods

Given the scope of the proposed study, a total sample size of 40 veterans is considered a realistic and achievable enrollment to generate pilot data. For AIM 1, a cross-sectional design that includes within-subjects (VETS conditions) and between-subjects (veteran groups) factors will be used to compare balance and posture in patients awaiting surgery for CSM ($n = 20$) to a cohort of age and gender-matched non-CSM controls ($n = 20$). The 20 veterans with CSM recruited for AIM 1 will also serve as the sample for AIM 2, which is a longitudinal assessment of balance following surgical intervention for CSM.

Drs. [name], [name] and [name] will identify potential participants for the CSM group by screening all CSM patients undergoing assessment and scheduling for surgical intervention. These potential participants will be referred to [name] study team, where a staff member will provide background information, additional pre-screening, and scheduling (if eligible and interested).

Healthy volunteers will be recruited using a poster/flyer within the SVAMC. Potentially interested participants will call the study staff, as prompted by the advertisement, and will undergo pre-screening and scheduling. A copy of this flyer may be found in the submission package. Healthy volunteers may also be recruited from the pool of participants who consented to future contact in the SMBI Data Repository. These individuals will be contacted by the research staff and will be asked if they are interested; the attached Telephone Script includes the language used for these participants.

For the cross-sectional arm of the study, veteran volunteers in the CSM and control conditions will be compensated \$40 for their participation. Veteran volunteers in the CSM group will have the opportunity to earn an additional \$40 for attending each of the three post-operative assessments, resulting in a maximum remuneration of \$160. Participants will be paid in full for all sessions attended, even if they cease participation before fully completing a session. Payment will be sent in the form of a VA check to the address specified by the participant.

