Demographics: The demographics form will ask about basic information, including: age, sex, history of head injury, and current medications.

VETS. Postural stability will be assessed with the VETS system devised by [name] ^{31, 38-40}. All postural conditions are performed in a darkened room. The physical set-up has the front edge of the Wii balance board (WBB) placed at a distance of 40 cm from a 60" commercially-available flat screen television. This device employs a custom-designed software user interface that allows wireless Bluetooth collection of

center-of-pressure data at 100 Hz with high test-retest reliability and immediate display of results. Excellent concurrent validity was determined by comparing VETS with a research grade gold-standard NeuroCom, which revealed $ICC > 0.90$ (min: 0.901, max: 0.995, $p < 0.01$).

The postural stability task will involve six conditions during which veterans are instructed to look straight ahead and maintain an upright stance as stably as possible (see Figure 2). Veterans are barefooted with feet comfortably placed ~25 cm apart. The six conditions are (1) Eyes Open (EO) Firm – eyes open with stable support surface (i.e. WBB) and static visual scene, (2) Eyes Closed (EC) Firm – eyes closed with stable support surface and dark screen, (3) Dynamic Scene (DYN) Firm – eyes open with a stable support surface while viewing a scene dynamically rotating in the roll (fronto-parallel) plane at 60 deg/s, (4) EO Foam - eyes open with unstable support (Airex foam pad placed on top of the WBB) and stable visual scene, (5) EC Foam – eyes closed with unstable support and dark screen, and (6) DYN Foam – eyes open with unstable support and rotating scene. Each condition lasts 30 secs and is repeated 3 times before progressing to the next condition. The conditions are tested in order 1-6, in a manner that emulates the validated Sensory Organization Test (SOT) protocol (Natus/Neurocom). For safety, an experimenter guards the veteran to protect against falls.

B. Procedure

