All statistical analyses will be performed using IBM SPSS Statistics Version 24 and MedCalc. For descriptive purposes, continuous data will be summarized with the number of non-missing values, mean, and standard deviation, minimum, median, and maximum and categorical data will be summarized with the number of non-missing values and the numbers (frequencies) of values equal to each of the possible categories, unless stated otherwise. Univariate analyses will examine data distributions, potential outliers and missing data. All statistical tests will be two-sided with a significance level of alpha=0.05. Unless otherwise stated, no multiplicity adjustment will be applied and no missing values will be imputed. For analysis of posturography data, each of the six VETS postural conditions (see Figure 2) will be tested three times for each participant from which an average is calculated for each condition. These within-subject, within-condition averages will be used in model building to assess between groups differences in balance (AIM 1a) and within-groups change in balance over time following surgical intervention (AIM 2).

For **AIM 1a**, mixed model ANOVA will be used to compare veteran group (CSM vs Control) and within-subject visual (EO, EC, and DYN) and surface conditions (FIRM and FOAM). Average COP sway, COP velocity, and MSE of COP sway velocity for each of the six VETS conditions will serve as dependent measures in separate models. Using Mauchly's tests, violations of sphericity will be detected, are corrected with Greenhouse-Geisser adjustments.

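### AIM 1a has no plan for head-injury history, which the protocol's own pilot associates with DYN-FOAM sway, so an imbalance could distort the CSM-control contrast there

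*Combined protocol and SAP*

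**What the plan says.** The AIM 1a paragraph of section 5.6 states that "mixed model ANOVA will be used to compare veteran group (CSM vs Control"), crossed with three visual conditions and two surfaces. No covariate is listed. Sections 5.1 and 5.4 match controls to CSM veterans on age and on gender or sex, and on nothing else.

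The demographics form in section 5.5 records "age, sex, history of head injury, and current medications". No analysis in section 5.6 uses the head-injury item, and section 5.5 has the form filled in after consent, at the first session.

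Section 2.0 reports the site's own pilot: "Veterans with lifetime history of mTBI exhibited greater COP sway area during the DYN-FOAM condition compared to HEALTHY veterans". The text beside it gives the triple interaction as F(1.176, 17.645) = 5.385, p = .028, and places the mTBI difficulty at DYN-FOAM in particular.

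Two statements bear on balance between the groups. On controls, section 5.2 says "Healthy volunteers may also be recruited from the pool of participants who consented to future contact in the SMBI Data Repository". On CSM, section 2.0 says "Those presenting to the emergency room for head trauma from falling were more likely to have CSM".

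Section 5.4 excludes a prior neurological disorder in any participant, exempting only lumbar spine disease and peripheral neuropathy. It names neither mTBI nor head injury.

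**The concern.** The pilot model has the same structure as AIM 1a: surface by visual condition by group. The term that separated mTBI from HEALTHY veterans is one that AIM 1a would read as a CSM effect. DYN-FOAM is also one of the three FOAM conditions in Hypothesis 1, and sway area is the primary measure.

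If one group carries more head injury, the difference at DYN-FOAM mixes two sources and the planned model cannot separate them. More head injury in the CSM group would inflate the apparent CSM effect; more among controls would mask it. The documents give a reason to expect the first (head trauma from falls is linked to CSM). They leave the second open, because the repository's contents are not described and the site is running a veteran mTBI study.

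**Working it through.** **1. The pilot figure.** With 10 + 7 = 17 veterans, the uncorrected degrees of freedom are 2 and 2 x 15 = 30. The Greenhouse-Geisser epsilon is 1.176 / 2 = 0.588, and 30 x 0.588 = 17.64, which agrees with the stated 17.645. The upper tail of F at 5.385 is 0.0279, which reproduces the stated .028.

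**2. An anchor for effect size.** The pilot gives no mean or SD, only p < .05 for the DYN-FOAM comparison. The smallest observed difference reaching that in a simple two-sample t-test is t(0.975, 15) x sqrt(1/10 + 1/7) = 2.131 x 0.493 = 1.05 SD. This is a threshold for the observed difference, not a lower bound on the true one, so a range of 0.5 to 1.5 SD is used.

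**3. Bias.** Expected bias = (head-injury effect in SD) x (difference in prevalence, CSM minus control). At 1.05 SD, a 20-point difference gives 1.05 x 0.20 = 0.21 SD and a 40-point difference gives 1.05 x 0.40 = 0.42 SD, with the sign set by the direction. The documents state no power calculation. Section 5.2 says only that "a total sample size of 40 veterans is considered a realistic and achievable enrollment to generate pilot data". A t-test of 20 vs 20 has 80% power at about 0.91 SD, so the bias is 0.21 / 0.91 = 23% to 0.42 / 0.91 = 46% of the detectable effect.

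**4. Type I error at DYN-FOAM.** Section 5.6 fixes the level: "All statistical tests will be two-sided with a significance level of alpha=0.05". The simulation used 40,000 runs per scenario, 20 per group, a single DYN-FOAM contrast and no true CSM effect. Prevalence is an assumption: 20% in the lower group.

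| Assumed effect | 20 points | 30 points | 40 points |
|---|---|---|---|
| 0.5 SD | 6% | 7% | 9% |
| 1.05 SD | 9% | 14% | 22% |
| 1.5 SD | 12% | 21% | 34% |

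Reversing the imbalance gives nearly the same rates. With head injury as a covariate, the bias is about 0 and the rate about 5% in every cell. If one group has no head injury and the other 40%, the unadjusted rates are 9%, 23% and 38%.

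**5. Power.** With a true CSM effect of 0.9 SD, a head-injury effect of 1.05 SD and a 20-point imbalance, unadjusted power is 48% if controls carry the excess and 87% if the CSM group does. Adjusted power is about 76% either way.

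**6. Chance imbalance.** If true prevalence is equal, at 20% to 50%, groups of 20 differ by 20 points or more in 16% to 27% of studies. This leaves the overall type I error at 5%, but it shifts the estimate in the study at hand. At 30% in both groups and a 1.05 SD effect, power is 71% unadjusted and 78% adjusted.

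**7. Averages over FOAM.** If only DYN-FOAM is affected, the mean of the three FOAM conditions carries a third of the bias: 0.21 / 3 = 0.07 to 0.42 / 3 = 0.14 of a single-condition SD at 1.05 SD. With equal SDs, correlations of 0.3 to 0.7 and a 31-point imbalance, the type I error is about 6% to 7%. Dilution is weaker if DYN-FOAM has the larger variance.

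**The case against.** The strongest reply is that eligibility may already deal with this. The exclusion of prior neurological disorder lists only two exemptions, and head injury is not one. Controls are called otherwise healthy, and the pilot used that label for a group kept separate from mTBI. This is a fair reading, but the text does not settle it. If it were applied to controls alone, the imbalance would become one-sided and inflate the CSM effect.

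A second reply is that head injury may partly result from CSM through falls, so adjusting for it could remove real CSM effect. This stands. It is a reason to report the adjusted model beside the planned one, not in place of it. The form's general head-injury item is also not identical to the pilot's lifetime mTBI classification.

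A third is that this is a 40-person pilot. That limits the severity, though an analysis of a collected variable is still cheap.

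Three stronger readings are tempting, and the documents do not support them. A reader might infer that mTBI causes greater DYN-FOAM sway, but 7 vs 10 veterans observed without randomisation show an association only. A reader might take the pilot's 7 of 17 as the head-injury prevalence to expect among controls, but it reflects the case mix of a study that compares veterans by mTBI history. A reader might conclude that Hypothesis 1 as a whole is compromised, but the pilot places the mTBI difference at DYN-FOAM, not in the EC or EO-Foam conditions.

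**Conclusion.** The point holds for the DYN-FOAM contrast and for the interactions of group with surface and visual condition. There, the planned model cannot distinguish a CSM effect from a head-injury imbalance in either direction. For assumed effects of 0.5 to 1.5 SD and imbalances of 20 to 40 points, type I error is about 6% to 34% unadjusted and about 5% adjusted. These figures rest on assumed prevalence and effect size and on a single-contrast t-test, not the full ANOVA. The actual imbalance is unknown and may be nil.

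FOAM averages are only mildly affected in the typical scenarios, the EC contrasts have no documented mTBI effect, and AIM 2 compares each veteran with himself or herself, so a fixed history does not confound it. This should be changed, but it does not invalidate the design.

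**What to change.** In section 5.6:

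- Tabulate head-injury history by group.
- Beside the planned AIM 1a ANOVA, pre-specify a model that adds head-injury history (yes/no) with its interactions with surface and visual condition.
- Pre-specify a repeat of the planned ANOVA without head-injured participants.
- State that a DYN-FOAM or interaction finding will be attributed to CSM only if it is consistent across these analyses. Judge consistency by the direction and size of the estimates, not by p < .05 in each.

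In section 5.4, state whether past mTBI falls under the neurological exclusion, and apply the answer in the same way to both groups.

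No new data are needed. The adjusted model takes one between-subject degree of freedom (38 to 37), and two from the error term of the triple interaction (2 x 38 = 76 to 2 x 37 = 74). The restricted analysis loses precision: at 40% vs 20% head injury it keeps 12 and 16 veterans, and the standard error factor rises from sqrt(1/20 + 1/20) = 0.316 to sqrt(1/12 + 1/16) = 0.382, about 21%. The remaining cost is possible over-adjustment if head injury partly follows from CSM-related falls, which is why the planned and adjusted results should appear together.

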Study of Postural Stability in Subjects with Myelopathy using a Portable Virtual Reality Balance Protocol

NCT03810781

Principal Investigator: [name]

Version Date: 9/5/19

Abstract

Veterans are at heightened risk of developing cervical spondylotic myelopathy (CSM) from rigors of military service. Diagnosis of CSM involves a set of clinical findings and is confirmed by imaging the spine.

Gait impairment and disturbances of stance control are hallmarks of CSM and are a consequence of abnormalities in proprioception due to dorsal column tract damage of the spine. Currently, gait and balance deficits rely on clinical level assessments and judgement for detection. An objective measure of posturography has the benefit of: a) quantifying balance-related disability in CSM, b) facilitating structure-functional assessments in CSM, and c) quantifying the degree surgical interventions affect posturography and recovery of function in CSM.

Objective and sensitive means for assessing balance and posturography exist, but are not routinely incorporated in diagnosis or functional tracking of progress after interventions such as surgery. A barrier may be accessibility of posturography and ease of assessments. The Virtual Environment TBI Screen (VETS) was devised using Army Rapid Innovation Development funding to objectively assess balance and posturography in a cost effective, but sensitive manner. VETS involves virtual environments and computerized posturography and is proving to be a sensitive system facilitating diagnosis, treatment, and mitigation of balance dysfunction associated with mTBI.

Our working hypothesis is VETS testing will enhance clinical judgements regarding CSM. This study is designed to provide data critical to a more extensive program of research incorporating posturography into treatment and rehabilitation of CSM. First, a limited comparative study of standing balance will be conducted of 20 veterans being evaluated for cervical spine surgery to treat CSM and 20 otherwise healthy veterans. Second, posturography of the 20 veterans undergoing surgery to treat CSM will be tracked during their scheduled follow up visits to determine the degree VETS scores are affected by surgery and to track recovery from CSM.

List of Abbreviations

ALS	amyotrophic lateral sclerosis
ANOVA	analysis of variance
AUC	area under the curve
COP	center of pressure
CSM	cervical spondylotic myelopathy
CT	computed tomography
DYN	Dynamic
EC	Eyes Closed
EO	Eyes Open

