For the purposes of illustration we compared the two MS veterans to HEALTHY veterans with a $2 \times 3 \times 2$ (Surface x Visual Condition x Clinical Group) mixed model analysis of variance (ANOVA) which yielded a significant triple interaction, $F(2,16) = 5.49, p = .014$. Specific comparisons between conditions showed the two eyes open conditions are similar to HEALTHY veterans ($p > .05$) suggesting for these MS veterans postural control motor outputs are normal. Differences were apparent in the EC conditions suggesting visual input is necessary to maintain balance. Further, the DYN-FOAM condition was compromised in the two MS veterans ($p < .05$), suggesting impaired ability to integrate visual, proprioceptive, and vestibular stimuli in MS. Comparison was also made between those with lifetime history of mTBI and HEALTHY veterans with a similar $2 \times 3 \times 2$ (Surface x Visual Condition x Clinical Group) mixed model ANOVA. The triple interaction was significant, $F(1.176, 17.645) = 5.385, p = .028$ (Greenhouse-Geisser correction for violations of sphericity). Those with lifetime history of mTBI exhibit balance difficulties specifically on the DYN-FOAM condition ($p < .05$). For MS and lifetime mTBI, balance was compromised during the DYN-FOAM condition, which is designed to produce to rollvection³³, that is, perceived self-motion due to conflicting visual, proprioceptive and vestibular inputs.

The ongoing research in veterans demonstrates the utility of the six conditions comprising VETS to expose motor, proprioceptive, vestibular, and integrative sensory deficits. The combination of conditions in VETS provide a means to advance research in CSM beyond that already conducted in civilians to date.

Imposition of posturography is envisioned to aid in clinical assessment in CSM in three meaningful ways: a) assessment of CSM severity, especially in cases of 'mild' CSM, b) differentiating CSM from other entities, c) providing an objective target to assess treatments interventions and recovery. For differential diagnosis, the conditions potentially distinguished by posturography are trauma, ALS³⁴, MS (Figure 2), syringomyelia, myelitis, and vitamin B12 deficiency³⁵ (See Table 1).

Table 1. Sensory Motor Deficits and Expected Impact to Posturography with VETS			
Motor	Proprioception	VETS Conditions	
CSM	?	?	EC, FOAM
Trauma	↓↓	↓↓	ALL
ALS	↓↓	Late Stages	ALL
MS	Late stages	↓↓	EC, DYN-FOAM
Syringomyelia	↓↓	Late Stages	ALL
Myelitis	varied	varied	

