3.0 Objectives

AIM 1A: Determine whether and to what degree balance is altered in CSM. The degree of COP sway will be compared between CSM and controls in the six conditions comprising VETS testing.

Hypothesis 1: Impaired proprioceptive transmission in CSM will result in poorer balance (larger COP sway area) during EC conditions (eliminating the ability to compensate with visual feedback) and FOAM (reducing the reliability of somatosensory feedback) conditions compared to healthy veterans.

AIM 1B: Determine whether VETS enhances sensitivity and selectivity in the diagnosis of CSM. Composite measures of balance will be related to clinical assessment tools and their relationship with MRI.

Hypothesis 2: VETS will provide additional sensitivity and selectivity in identifying CSM compared to current clinical assessment tools.

Hypothesis 3: The degree of COP sway area during EC and FOAM conditions is expected to directly relate to the degree of spinal cord compression quantified from MRI, leading to a more sensitive gradation in the severity of CSM.

AIM 2: Evaluate the VETS scores after surgery for CSM. The degree of COP sway area under the 6 conditions will be compared before surgery, 2 weeks, 6 weeks, and 6 months after surgery.

Hypothesis 4: We expect surgery to reduce COP sway in EC conditions

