5.4 Inclusion/Exclusion Criteria

Inclusion criteria for the CSM group are:

- Symptoms of myelopathy in upper and lower extremities and stenosis of the cervical spine demonstrated by MRI or myelography
- Lower extremity muscle strength of 4 as quantified by manual muscle test (MMT) or above
- Ability to stand without support with eyes closed for 30 seconds or more.

Exclusion criteria for all study participants are:

- History of neurological disorder other than lumbar spine disease or peripheral neuropathy
- Inability to stand in an upright position with both feet together and eyes closed.

Veterans in the control group will be recruited via printed advertisement or through the SMBI Data Repository and age- and sex-matched with CSM veterans. Every effort will be made to ensure that the veteran participants enrolled in the proposed study are reflective of the VA population, with regard to sex and race/ethnicity. If any participant over the age of 89 happens to enroll, their exact age will be recorded as >89.

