For **AIM 1b**, receiver operating characteristic (ROC) analyses will be conducted as a preliminary determination of sensitivity and specificity of VETS conditions to detect CSM. We will assess areas under the curve (AUC) and corresponding 95% confidence intervals, which will serve as indices of accuracy for CSM diagnosis. Using known groups (CSM and control veteran volunteers), we will compare AUC curves corresponding to 1) traditional diagnostic scale measures (e.g., mJOA scale, Nurick Scale, NDI, and SF-36), 2) VETS conditions, and 3) scale measures combined with VETS conditions. These analyses will serve as indicators for the degree the posturography, alone or in combination with scale measures, are sensitive and selective to CSM. An AUC = 0.50 will be considered chance level for correct classification into CSM and control groups. Differences in AUC for each of the three ROC curves will be accomplished using methods described by Delong et al ⁴⁵.

For **AIM 2**, VETS data for CSM veterans will be assessed for changes in balance following surgical intervention. VETS dependent measures outlined above will be entered into repeated-measures ANOVA with time point (pre-surgery, 2 weeks, 6 weeks, and 6 months post-surgery) entered as an additional repeated measure. Using Mauchly's tests, violations of sphericity will be detected, are corrected with Greenhouse-Geisser adjustments.

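### Aim 1b reads known-group separation of surgery-track CSM from healthy veterans as diagnostic accuracy, and its comparison with the Nurick and mJOA scales is partly circular

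*Combined protocol and SAP*

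**What the plan says.** The Abstract describes the comparison as one of "20 veterans being evaluated for cervical spine surgery to treat CSM and 20 otherwise healthy veterans". Section 5.4 requires of each case "Symptoms of myelopathy in upper and lower extremities and stenosis of the cervical spine demonstrated by MRI or myelography", with lower-limb strength of at least grade 4 and the ability to stand with eyes closed. For all participants it excludes neurological disorders other than lumbar spine disease and peripheral neuropathy. Section 5.2 recruits controls as healthy volunteers, by flyer or from a data repository.

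For Aim 1b, section 5.6 introduces the ROC analysis "as a preliminary determination of sensitivity and specificity of VETS conditions to detect CSM". It then says of the AUCs and their confidence intervals, "which will serve as indices of accuracy for CSM diagnosis", and continues: "Using known groups (CSM and control veteran volunteers), we will compare AUC curves" for the scales (mJOA, Nurick, NDI, SF-36), for VETS, and for both together, tested by the DeLong method. Hypothesis 2 in section 3.0 reads: "VETS will provide additional sensitivity and selectivity in identifying CSM compared to current clinical assessment tools". Aim 1B adds: "Composite measures of balance will be related to clinical assessment tools and their relationship with MRI".

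The Introduction (section 2.0) sees posturography as helping to grade severity, above all in mild CSM, and as "differentiating CSM from other entities".

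**The concern.** There are two problems, both arising from who is in the sample.

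First, an AUC between patients already diagnosed and on the way to surgery and people recruited because they are healthy answers an easier question than diagnosis does. In use, the test would meet suspected or mild CSM and other patients with poor balance. Reporting the AUC as diagnostic accuracy invites the planned larger study to build on a value that may not hold there.

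Second, Hypothesis 2 asks VETS to improve on scales that score the symptoms by which cases were selected. If those scales already separate the groups almost perfectly, a finding that VETS adds nothing would reflect the comparator and not VETS, and a useful measure could be dropped for the wrong reason.

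**Working it through.** The documents state no expected AUC, power or precision for Aim 1b, so there is no figure to reproduce. The sample of 40 rests on feasibility (section 5.2). All AUCs and correlations below are assumptions, shown as ranges.

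**1. What Nurick and mJOA can show (sections 5.4 and 5.5).** Section 5.5 defines Nurick grade 0 as no evidence of cord disease. Section 5.4 requires myelopathy symptoms in every case, so cases should grade 1 or more and a healthy control, if graded, 0. That gives an AUC of 1, or close to it. For mJOA the item maxima are 5 + 7 + 3 + 3 = 18, meaning no dysfunction. If all controls score 18 and a share q of cases score below 18, then AUC = q + (1 − q)/2 = 1 − (1 − q)/2:

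| q | mJOA AUC | Most that VETS could add |
|---|---|---|
| 0.80 | 0.90 | 0.10 |
| 0.90 | 0.95 | 0.05 |
| 0.95 | 0.975 | 0.025 |
| 1.00 | 1.00 | 0 |

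The procedure in section 5.5 has the study doctors complete these two scales for CSM patients at standard-of-care visits and describes no rating of controls. Without control values the Nurick and mJOA curves are undefined; with assigned normal values they are near perfect by construction. NDI and SF-36 are self-reported, and all participants complete the self-report questionnaires at the first session.

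**2. Chance of showing that VETS adds.** The planned paired DeLong test was simulated with 20 per group, two-sided 0.05 and 3,000 runs per setting. Scale and VETS scores were normal with equal variances, VETS AUC was 0.80 or 0.85, and the within-group correlation was 0 or 0.3. The combination used known optimal weights, and only rejections in its favour were counted.

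| Scale AUC | True gain from VETS | Power |
|---|---|---|
| 0.75 to 0.80 | 0.052 to 0.142 | 15 to 53% |
| 0.90 | 0.014 to 0.050 | 3 to 16% |
| 0.95 | 0.004 to 0.024 | 0.4 to 3% |
| 0.975 | 0.001 to 0.012 | 0.3% or less |

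Weights fitted in the same 40 people would push the combined AUC upward, which is a separate problem not covered here.

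**3. How the AUC moves with the case mix.** With equal-variance normal scores, AUC = Φ(d/√2), so d = √2·Φ⁻¹(AUC). For an AUC of 0.85, d = 1.47. Half of that is about 0.73, and Φ(0.73/√2) = 0.70. In the same way, VETS AUCs of 0.80, 0.85, 0.90 and 0.95 in this sample fall to 0.66, 0.70, 0.74 and 0.80 if milder cases show half the separation. Against a look-alike disease with equal sway the AUC is 0.50. In the protocol's own Table 1, the eyes-closed condition is expected to be affected in both CSM and MS.

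**4. Precision.** The Hanley-McNeil standard error with 20 per group is 0.071 at AUC 0.80 (95% CI 0.66 to 0.94) and 0.062 at 0.85 (0.73 to 0.97).

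**The case against.** The plan is candid about much of this. It calls the ROC analysis preliminary, the groups known and the data pilot data, and it defines chance as classification into CSM and control groups. That softens the claim, but the sentence on accuracy for diagnosis still stands and nothing limits it.

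A reader might infer that the study promises to separate CSM from MS or ALS and must fail. The documents do not support that: this is an envisioned use in the Introduction, not an aim or hypothesis. What stands is that the AUC carries no information on it.

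A reader might also infer that the sample consists of extremes. Section 5.4 sets no disability threshold, does not exclude mild CSM, and removes the weakest patients through its strength and standing criteria. Controls are matched on age and sex and may have lumbar disease or neuropathy. The case mix is still unrepresentative of suspected CSM, but it is not purely extreme.

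Finally, a reader might infer that a gain from VETS cannot appear at all. That goes too far. The ceiling follows from the definitions for Nurick and is likely for mJOA, but it is less certain for NDI and SF-36. Even with scale AUCs of 0.75 to 0.80, power is only 15 to 53%, so the small sample limits Hypothesis 2 without any ceiling.

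Comparing and combining the scales with VETS is one way to relate balance to the clinical tools. It does not show whether sway follows severity among patients.

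**Conclusion.** The concern holds in this form. Aim 1b estimates known-group separation and should not be read as diagnostic accuracy. The direction of the error for milder or suspected CSM is likely upward. Its size cannot be computed from the documents, and any single figure for the overstatement would rest entirely on assumed separations.

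The Hypothesis 2 comparison is partly circular for Nurick and probably for mJOA, whose AUCs will be near 1 or undefined. An added contribution from VETS is then very unlikely to be detectable: power is at most about 3% at a scale AUC of 0.95, under the assumed VETS AUCs and correlations. This rests on controls being unrated or rated normal on those scales.

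Section 5.6 also has no analysis within the CSM group relating sway to the clinical scales, which is the plain reading of the Aim 1B sentence. The matter is worth correcting because a larger programme is to be built on these results.

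**What to change.** 1. In section 5.6, Aim 1b, replace the statement that the AUCs index diagnostic accuracy with: *indices of known-group separation between surgery-scheduled CSM and healthy veterans; not an estimate of diagnostic accuracy or differential diagnosis*. Restate Hypothesis 2 as: *VETS adds to the separation of these known groups achieved by the scales*.
2. State that failure of VETS to add to mJOA or Nurick in this sample is not evidence against its added value. Base the VETS-versus-scales AUC comparison on NDI and SF-36, which both groups complete.
3. Add, within the 20 CSM patients, descriptive Spearman correlations with 95% CIs of baseline sway area in the eyes-closed and foam conditions with mJOA total, mJOA lower-extremity score and Nurick grade.

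An AUC for the less impaired half of the cases is tempting but should not be added. With about 10 cases against 20 controls and an AUC of 0.77, the Hanley-McNeil standard error is about 0.10 (95% CI 0.58 to 0.96), too wide to show whether accuracy falls in mild disease.

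The cost is protocol wording and a few descriptive analyses of data already planned, with no new patients. The claim becomes more modest and the correlations will be imprecise. For r = 0.4 and n = 20, the Fisher approximation gives atanh(0.4) ± 1.96/√17 = 0.424 ± 0.475, a 95% CI of about −0.05 to 0.72.
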